2.1. Part A: 52-Week Double-Blind Treatment Phase Objectives

2.1.1. Primary Objective

The primary objective of this study is to investigate the efficacy of sirukumab (100 mg every 2 weeks [q2w] for 12 months) as compared to placebo, each administered in addition to a 6-month prednisone treatment regimen in the 52-week double-blind treatment phase (Part A), i.e. Arm A vs. Arm D as per [Table 2](#).

2.1.2. Secondary Objectives

The secondary efficacy endpoints of this study are:

To assess cumulative prednisone doses in subjects treated with sirukumab plus prednisone as compared to placebo plus prednisone

To investigate the efficacy of:

1. Sirukumab (100 mg q2w for 12 months) administered with a 3-month prednisone treatment regimen versus placebo administered with a 6-month prednisone treatment regimen, i.e. Arm B vs. Arm D as per [Table 2](#).
2. Sirukumab (100 mg q2w for 12 months) administered with a 6-month prednisone treatment regimen as compared to placebo administered with a 12-month prednisone treatment regimen (standard of care), i.e. Arm A vs. Arm E as per [Table 2](#).
3. Sirukumab (100 mg q2w for 12 months) administered with a 3-month prednisone treatment regimen versus placebo administered with a 12-month prednisone treatment regimen, i.e. Arm B vs. Arm E as per [Table 2](#).
4. Sirukumab (50 mg every 4 weeks [q4w] for 12 months) as compared to placebo, each administered in addition to a 6-month prednisone treatment regimen, i.e. Arm C vs. Arm D as per [Table 2](#). Sirukumab (50 mg q4w for 12 months) administered with a 6-month prednisone treatment regimen as compared to placebo administered with a 12-month prednisone treatment regimen, i.e. Arm C vs. Arm E as per [Table 2](#).

To characterize sustained remission over time

To characterize disease flare over time

To assess the effect of sirukumab treatment on health-related quality of life, GCA and steroid-related symptoms and disability by patient and physician reported outcomes over time

To characterize changes in biomarkers of disease activity.

2.1.2.1. Safety Objectives

To evaluate the safety of sirukumab plus prednisone treatment compared to placebo plus prednisone treatment

To investigate corticosteroid-related toxicities.

2.1.2.2. Pharmacokinetic/Immunogenicity Objectives

To investigate the pharmacokinetics of subcutaneously administered sirukumab

To evaluate the immunogenicity of subcutaneously administered sirukumab

2.1.2.3. Pharmacodynamic Objectives

To characterize the effect of sirukumab on IL-6 levels in the blood.

2.1.2.4. Exploratory Objectives

To explore the effect of sirukumab on exploratory biomarkers of Th1 and Th17 cell function

To evaluate the effect of sirukumab on exploratory biomarkers of bone metabolism

To explore the utility of vascular ultrasound (US) imaging assessment of inflammation in temporal and axillary arteries as an indicator of disease activity in a cohort of study subjects

To explore the predictive value of US for clinical efficacy in GCA.

2.1.2.5. Pharmacogenetic Objectives

To potentially explore relationships between genetic variants and sirukumab efficacy and safety endpoints.

2.2. Part B: 104-Week Long-Term Extension Phase Objectives

The objectives for Part B, the 104 week long-term extension phase are:

To evaluate the long-term maintenance of disease remission on cessation of 12 months of sirukumab treatment

To assess the effect of sirukumab treatment on health-related quality of life, GCA and/or steroid-related symptoms and disability by patient and clinician reported outcomes over time

To assess the long-term cumulative prednisone doses

To assess the long-term safety of sirukumab

To investigate long-term corticosteroid-related toxicities

[figure not shown]
To evaluate the immunogenicity of subcutaneously administered sirukumab in subjects receiving open-label sirukumab.

3. Investigational Plan

3.1. Overall Study Design and Plan

This is a multicenter, randomized, double-blind, placebo-controlled study to evaluate the efficacy and safety of 2 doses of sirukumab in the treatment of GCA. The study design is summarized in [Figure 1](#).

Figure 1 Study Design

q2w=every 2 weeks; q4w=every 4 weeks

The study will be conducted in 2 distinct parts (Part A and Part B) and consists of the following phases:

- A screening phase of up to 6 weeks in duration.
- Part A: A 52-week double-blind treatment phase to establish the efficacy and safety of sirukumab in the treatment of GCA.
- Part B: A 104-week long-term extension phase with the option to receive open-label sirukumab (up to a 52-week duration of open-label treatment) for subjects with active disease at the end of Part A, subjects who have not been able to follow the prednisone taper during Part A, or those who newly flare during the first 52 weeks of Part B.
- An up to 16-week follow-up phase to ensure that all subjects are evaluated for safety at least 16 weeks after receiving the last dose of study drug. This will apply to subjects who are withdrawn prematurely from the study or whose open-label treatment with sirukumab in Part B will complete after Week 88. The duration of the follow-up may vary depending on the time point when the last dose of study drug is taken. Only subjects who complete their sirukumab treatment at Week 104 will require the full 16-week follow-up period.

The maximum duration of subject participation (including screening) is 178 weeks. Completion of Part A is defined as completion of the 52 weeks of double-blind treatment. Completion of Part B is defined as completion of the 104 weeks of the extension phase. Completion of the study is

defined as completion of both Parts A and B of the study and/or completion of the up to 16-week follow-up phase if applicable.

The study population will be comprised of approximately 204 subjects with a diagnosis of GCA based on the Revised GCA Diagnosis Criteria. Both new onset (diagnosis within 6 weeks of Baseline) and relapsing/refractory (established diagnosis greater than 6 weeks prior to Baseline with disease activity within 6 weeks of Baseline) GCA subjects will be eligible.

Eligible subjects will be required to have active disease within 6 weeks prior to the Randomization (Baseline) visit. Active disease is defined as the presence of unequivocal clinical signs and symptoms attributable to GCA and an erythrocyte sedimentation rate (ESR) ≥ 30 mm/hr and/or serum C-reactive protein (CRP) ≥ 1 mg/dL (10 mg/L).

For more details on the schedule of assessments, please refer to [Section 13.1](#).

3.2. Study Endpoints

Due to the sponsors decision to terminate the study and the data not being available the following endpoints will not be reported in this planned analysis:

- Pharmacokinetic endpoints
- Immunogenicity endpoints
- Pharmacodynamic endpoints
- Pharmacogenetics endpoints
- Vascular ultrasound endpoints: Even though 3 subjects were randomized to the US imaging portion of the study, only one patient passed the Week 12 visit. There was no sufficient data collected to perform any analysis, so no data for this cohort of subjects will be reported.

The pharmacokinetic, immunogenicity, pharmacodynamic (IL-6) and pharmacogenetics samples will not be analyzed, therefore there will be no data related to these endpoints and these objectives that can be reported.

Additionally:

- All available data for exploratory endpoints related to biomarkers such as IFN- γ , CTX1 and PINP will only be listed.
- No statistical analysis will be carried out for efficacy endpoints due to the limited number of subjects completing the study at Week 52.

However, [Section 3.2.1](#) and [Section 3.2.2](#) list endpoints as specified in the protocol.

3.2.1. Study Endpoints for Part A

3.2.1.1. Primary Efficacy Endpoint

The primary endpoint of this study is the proportion of subjects in sustained remission at Week 52, defined as having achieved all of the following:

1. Remission at Week 12, where remission is defined as:

- a. Clinical remission at Week 12, defined as absence of signs and symptoms of GCA and
 - b. Normalization of ESR [$<30\text{mm/hr}$] and CRP [$<1\text{mg/dL}$]
- AND**
2. Absence of disease flare following remission at Week 12 through Week 52, where disease flare defined as recurrence of symptoms attributable to active GCA, with or without elevations in ESR and/or CRP
- AND**
3. Completion of the assigned prednisone taper protocol
- AND**
4. No requirement for rescue therapy at any time through Week 52

3.2.1.2. Secondary Efficacy Endpoints

- Cumulative prednisone dose over time
 - Proportion of subjects in sustained remission at each time point of assessment from Week 12 to Week 52, where sustained remission is defined as having achieved all of the following at each visit:
 1. Remission at Week 12:
 - a. Clinical remission at Week 12, defined as absence of signs and symptoms of GCA
And
 - b. Normalization of ESR [$<30\text{mm/hr}$] and CRP [$<1\text{mg/dL}$]
- AND**
2. Absence of disease flare following remission at Week 12 through Week X, disease flare defined as recurrence of symptoms attributable to active GCA, with or without elevations in ESR and/or CRP
- AND**
3. Adherence to the assigned prednisone taper protocol through Week X,
- AND**
4. No requirement for rescue therapy at any time through Week X
- Time to first disease flare after clinical remission
 - Number of disease flares per subject over time
 - Proportion of subjects requiring hospitalizations for disease flare and number of hospitalizations for disease flare over time
 - Patient-reported outcomes (PRO) including 36-item Short Form health survey version 2 (SF-36 v2) acute, EuroQol – 5 dimensions, 5 levels (EQ-5D-5L), Functional Assessment of Chronic Illness Therapy-fatigue (FACIT-Fatigue), Pain Numeric Rating Scale (NRS), Steroid Impact Questionnaire, Health Assessment Questionnaire – Disability Index (HAQ-DI), Patient Global Impression of Change (PGIC), Patient Global Assessment of disease activity (PtGA)

- Clinician-reported outcomes: Physician Global Assessment of disease activity (PhGA)
- Change from Baseline in ESR over time
- Change from Baseline in serum CRP over time

3.2.1.3. Safety Endpoints

- Incidence of adverse events (AEs) and serious AEs (SAEs), incidence of corticosteroid-related AEs, changes in vital signs, hematology and clinical chemistry parameters

3.2.1.4. Pharmacokinetic / Immunogenicity Endpoints

- Serum concentrations of sirukumab
- Serum anti-sirukumab antibodies

3.2.1.5. Pharmacodynamic Endpoints

- Change from Baseline in free and total IL-6 over time

3.2.1.6. Exploratory Endpoints

- Change from Baseline in interferon (IFN)- γ and IL-17A
- Change from Baseline in serum markers of bone formation/resorption: carboxyterminal cross-linked telopeptide of bone collagen (CTX)1/procollagen type 1 N-propeptide (P1NP)
- Change over time in measurements of vascular inflammation in temporal and axillary arteries
- Correlation of clinical endpoints with changes in vascular inflammation.
- Correlation of changes in vascular inflammation on US with clinical activity, CRP and ESR
- Correlation of changes in vascular inflammation on US with health-related quality of life outcomes

3.2.1.7. Pharmacogenetic Endpoints

- Correlation of genetic markers with the safety and efficacy response to sirukumab. This endpoint will not be addressed in this document

3.2.2. Study Endpoints for Part B

- Proportion of subjects who remained in sustained remission without requirement for rescue therapy or treatment change at Week 24 of Part B
- Proportion of subjects in sustained remission over time
- Time to first disease flare for subjects in sustained remission at Baseline of Part B
- Number of disease flares per subject over time
- Proportion of subjects requiring hospitalizations for disease flare and number of hospitalizations for disease flare over time

- Proportion of subjects who remained in sustained remission without requirement for rescue therapy or treatment change 6 months after cessation of 12-month sirukumab treatment
- Patient-reported outcomes including SF-36v2 acute, EQ-5D (5L), FACIT-Fatigue, Pain NRS, Steroid Impact Questionnaire, HAQ-DI and PtGA
- Clinician reported outcomes including PhGA
- Cumulative prednisone dose over time
- Incidence of AE and SAEs, and changes in vital signs and hematology and clinical chemistry parameters
- Incidence of corticosteroid-related AEs
- Evaluation of serum anti-sirukumab antibodies

3.3. Treatments

Two doses of sirukumab (100 mg subcutaneous [SC] q2w and 50 mg SC q4w) were selected based on doses which have demonstrated efficacy in a Phase II study of rheumatoid arthritis subjects and are presently under investigation in Phase III studies for the treatment of moderate to severe rheumatoid arthritis. The 100 mg SC q2w dose of sirukumab has shown numerical superiority at 24 weeks in some efficacy endpoints (American College of Rheumatology criterion ACR20, change in disease activity score) over other sirukumab doses tested in the Phase II study and may be more likely to provide a clinically meaningful response in an IL-6– mediated disease such as GCA. The 50 mg q4w dose of sirukumab will also be evaluated to more fully characterize the benefit-to-risk profile of sirukumab in GCA.

Following the screening period, eligible subjects will be randomized to receive sirukumab (100 mg SC q2w or 50 mg SC q4w) or matching placebo. All subjects will receive prednisone during the 52-week double-blind treatment period according to a pre-specified taper regimen.

Table 1 Investigational Product and Other Study Treatment

Product name	Study Treatment		
	Sirukumab	Placebo	Prednisone/ prednisone placebo
Dosage form	1.0 mL prefilled syringe	1.0 mL prefilled syringe	Tablets
Unit dose strength(s) / dose level(s)	100 mg/mL or 50 mg/mL	--	Up to-60 mg/day
Route of administration	SC	SC	Oral
Dosing instructions	SC q2w (treatment arms A & B) SC q4w (treatment arm C)	SC q2w (treatment arms D & E)	20-60 mg/day open-label, then 0-18 mg/day taper (blinded)

SC=subcutaneous; q2w=every 2 weeks; q4w=every 4 weeks.

Note subjects randomized to treatment arm C will alternate between sirukumab 50 mg SC and matching placebo SC injections in order to maintain the blind.

In Part A, eligible subjects will be randomized in a ratio of 3:3:2:2:2 to one of the 5 treatment arms described in [Table 2](#). The treatment descriptors and column headings in [Table 2](#) will be used in all data displays.

Table 2 Treatment Descriptors and Column Headings for Part A

Treatment Group	Treatment Descriptor	Column Header
Arm A	Sirukumab 100 mg SC q2w for 52 weeks plus a prespecified maximum of 6-month prednisone taper regimen	Sirukumab 100mg SC q2w + 6 month prednisone
Arm B	Sirukumab 100 mg SC q2w for 52 weeks plus a prespecified maximum of 3-month prednisone taper regimen	Sirukumab 100mg SC q2w + 3 month prednisone
Arm C	Sirukumab 50 mg SC q4w for 52-weeks plus a prespecified maximum of 6-month prednisone taper regimen	Sirukumab 50mg SC q4w + 6 month prednisone
Arm D	Placebo SC q2w for 52 weeks plus a prespecified maximum of 6-month prednisone taper regimen	Placebo SC q2w + 6 month prednisone
Arm E	Placebo SC q2w for 52 weeks plus a prespecified maximum of 12-month prednisone taper regimen	Placebo SC q2w + 12 month prednisone

It is important to note that prednisone intake will be recorded from different sources:

- Prednisone taken prior to screening: recorded on the “Prior Concomitant Medications - (Screening)” eCRF page

- Prednisone taken as part of the pre-specified taper (prednisone study drug):
 - Open-label portion – recorded in “Prednisone - Open Label” eCRF page
 - Blinded portion – recorded in “Prednisone - Blinded Taper” eCRF page
- Concomitant Prednisone – recorded on the “Concomitant Medications – Corticosteroids” eCRF page.

For more details, please refer to [Section 7](#).

Two types of rescue medication can be identified:

- Those from the “Concomitant Medications – Non Corticosteroids” eCRF page when the questions regarding Rescue Medication is ticked as "Yes" and the drug identified as GCA-related
- Those from the “Concomitant Medications – Corticosteroids” eCRF page when the question regarding Rescue Medication is ticked as "Yes" and the unit is not:
 - Actuation
 - Application
 - Area under curve
 - Cubic centimeter
 - Cells
 - Cells per kilogram
 - Fingertip unit
 - Drops
 - Gum
 - Inhalation
 - Kilocalories
 - Minimum alveolar concentration
 - Mega becquerels (MBq)
 - Millicurie
 - Nebule
 - Patch
 - Powder
 - Puff
 - Ring
 - Spray
 - Suppository

All subjects will be receiving background prednisone therapy. Subjects with relapsing/refractory GCA will have active disease despite previous or concurrent steroid therapy. Prednisone treatment must be initiated at Screening for subjects not currently receiving steroid treatment. Subjects should be reminded to discontinue any other prednisone or corticosteroid treatment and take only the prednisone study treatment. The prednisone dose for all subjects at Screening will be determined by the investigator and may be adjusted in an open manner based on the subject’s disease status per investigator discretion. An increase in prednisone dose may be required for some subjects currently receiving therapy to stabilize their disease activity prior to randomization. Investigators may consider if higher doses of prednisone are warranted for subjects with visual manifestations. All subjects must be receiving prednisone (a minimum dose of 20 mg/day) at the start of Screening. Prednisone treatment must be initiated at Screening for subjects not currently

receiving steroid treatment. At Baseline (Randomization), prednisone doses must be within 20-60 mg for the starting dose when the prespecified prednisone taper is initiated. The prespecified prednisone tapering schedule is outlined in [Table 3](#).

The standardized prednisone taper regimen will be open-label with identical weekly decreases in dose according to the starting dose for all subjects, until subjects reach a dose of 20 mg/day. Thereafter, prednisone dosing will be blinded to allow the pre-specified differences in tapering. Requirements for the prednisone taper are as follows:

- Subjects will remain on the prednisone dose they are currently receiving at Baseline (Week 0) for one week.
- At Week 1, the prednisone dose will be decreased in accordance with the prespecified prednisone taper schedule ([Table 3](#)).
- The pre-specified maximum tapering schedule to be followed will depend on the subject's treatment group assignment.
- The prednisone taper will be unblinded initially (open-label) and will consist of identical weekly decreases in dose for all subjects until a dose of 20 mg/day is reached, at which point the blinded portion of the prednisone tapering regimen will commence.
- Subjects who are receiving a prednisone dose of 20 mg/day at Baseline (Week 0) should continue taking the open-label 20 mg daily dose for one week. At Week 1, these subjects will initiate the blinded taper regimen.

Subjects unable to follow the prednisone taper due to disease flare, adrenal insufficiency, or safety reasons will cease the blinded prednisone treatment and will be offered treatment with an investigator-defined, open-label corticosteroid rescue regimen in combination with double-blind injections of sirukumab or placebo for the full 52 weeks, without a requirement to withdraw from the study. This study has been designed to allow subjects who are unable to follow the prednisone taper to continue in the study and follow the assessments at each visit as specified in the protocol.

When considering use of rescue prednisone, investigators should carefully assess whether the symptoms are related to an inflammatory GCA flare which would signify failure of tapering or is more likely due to non-inflammatory symptoms which could represent adrenal insufficiency or other co-morbidities.

All subjects who complete Part A of the study will be eligible to enter Part B. The 2 populations of subjects expected to enter into Part B are:

- Subjects in remission at the primary 52-week endpoint. These subjects will discontinue the blinded study drug treatment on entry into Part B and will be followed for maintenance of response. However, in the event of a disease flare, they will have the option to receive, at the discretion of the investigator, open-label sirukumab 100 mg SC q2w for a maximum of 52 weeks during the first 52 weeks of Part B.
- Subjects not in remission, at the primary 52-week endpoint, or subjects who have not been able to taper prednisone during Part A. Upon entry into Part B, these subjects will have the option to receive, at the discretion of the investigator, open-label sirukumab 100 mg SC q2w for a maximum of 52 weeks.

For subjects who newly flare at any time during the first 52 weeks of Part B and require a treatment change, open-label sirukumab 100 mg SC q2w can be initiated within the first 52 weeks of Part B. The duration of treatment will be at the discretion of the investigator but must not exceed 52 weeks.

Treatment with open-label sirukumab 100 mg SC q2w must complete by Week 104 (the end of the extension phase). Corticosteroid use or the initiation of methotrexate therapy alone or in addition to sirukumab treatment during Part B will be at the discretion of the investigator.

Investigators should carefully consider the individual benefit-risk of continuing sirukumab in those subjects who continue to experience flares or persistent disease activity following the start of open-label treatment.

Upon study completion, decisions on treatment options for individual subjects will be at the discretion of the investigator.

Table 3 Prednisone Taper

	Up to 3 Months	Up to 6 Months	Up to 12 Months
Open-Label taper	60	60	60
	50	50	50
	40	40	40
	35	35	35
	30	30	30
	25	25	25
	20	20	20
Blinded taper	15	15	18
	10	13	17
	5	12	15
	3	10	15
	1	9	13
	0	8	10
	0	7	10
	0	6	10
	0	6	10
	0	5	9
	0	5	9
	0	4	9
	0	4	9
	0	3	8
	0	3	8
	0	2	8
	0	2	8
	0	1	7
	0	1	7
	0	0	7
	0	0	7
	0	0	6
	0	0	6
	0	0	6
	0	0	6
	0	0	5
	0	0	5
	0	0	5
	0	0	5
	0	0	4
	0	0	4
	0	0	4
	0	0	4
	0	0	3
	0	0	3

	Up to 3 Months	Up to 6 Months	Up to 12 Months
	0	0	3
	0	0	3
	0	0	2
	0	0	2
	0	0	2
	0	0	2
	0	0	1
	0	0	1
	0	0	1
	0	0	1

Note: Individual subjects will be receiving differing doses of prednisone at specified time points. Therefore, the tapering schedule indicates the required decrease in prednisone dose on a weekly basis, with the specific week varying by individual subject.

3.4. Dose Adjustment/Modifications

No dose adjustment of sirukumab will be allowed in this study.

4. General Statistical Considerations

All analyses detailed in this SAP will be conducted using Statistical Analysis System (SAS)[®] statistical analysis software version 9.3 or higher (SAS Institute, Inc., Cary, North Carolina, USA). All SAS programs used to generate analytical results will be developed and validated according to PPD SAS programming standards and validation procedures.

Summary data will be presented in tabular format by treatment. Continuous variables will be summarized by descriptive statistics including number of subjects (N), mean, standard deviation (SD), median, minimum, and maximum.

Mean and median will be displayed to 1 more decimal place than the measured value. The SD will be displayed to 2 more decimal places than the measured value. Minimum and maximum will be displayed to the same decimal place as the measured value.

Categorical data (such as sex) will be summarized by number and percentage of subjects in each category. Percentages will be suppressed when the count is zero. A row denoted “Missing” will be included in count tabulations where necessary to account for missing values. The denominator for all percentages will be the number of subjects within the treatment (randomized or actual) group for the analysis set of interest, unless otherwise specified. Percentages which differ from 100% will be presented to 1 decimal place and 100% will be presented without a decimal.

Change from Baseline is the post-baseline value minus the baseline value. If the baseline or post-baseline value is missing, then the change from baseline is set to missing. For each scheduled post-baseline time point where change from Baseline is evaluated for continuous variables, descriptive statistics will be displayed for the values at Baseline, values at the scheduled post-baseline time point, and values for change from Baseline at the scheduled post-baseline time point for the set of subjects who have data at both Baseline and the time point being assessed. Early withdrawal visits as well as 16-week follow-up visits are considered as scheduled visits.

In case of multiple assessments for a scheduled visit, the last non missing assessment for this visit will be used for the summaries over time. All results will be listed.

Data will be displayed in all listings sorted by treatment (randomized or actual depending on the analysis set of interest) group and then subject number and visit, if applicable. In cases where more ordering is required, other variables will be included in the sort order as applicable. Subjects will be identified in the listings by the subject identification number concatenated with the investigator number. Any repeat or additional assessments performed will be included in the individual subject data listings.

For outputs displaying duration in weeks, a week will equal 7 days. For outputs displaying duration in months, a month will be defined as $(365.25/12) = 30.4375$ days, which is not equal to 4 weeks.

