<0.5 x 10  /μL (SI: <0.5 x 10  cells/L)	Interrupt study drug administration, repeat ANC test as soon as possible* If confirmed to be <0.5 x 10  /μL, discontinue study drug permanently (see Section 5.4.2)
Low Platelet Count	
Platelet count	Action
50,000 to ≤100,000/μL (SI: 50 to ≤100 x 10  cells/L)	Interrupt study drug administration, repeat platelet count test as soon as possible* May resume study drug when platelet count >100,000/μL
<50,000/μL (SI: <50 x 10  cells/L)	Interrupt study drug administration, repeat platelet count test as soon as possible* If confirmed to be <50,000/μL, discontinue study drug permanently (see Section 5.4.2)

\* Retesting should be performed by Central laboratory

Note: A WBC evaluation may include any abnormal cells, which will then be reported by the laboratory. Any RBC evaluation may include abnormalities in the RBC count and/or RBC parameters and/or RBC morphology, which will then be reported by the laboratory. In addition, any other abnormal cells in a blood smear will also be reported.

Any abnormalities in MCH, MCHC and MCV will be reported by the laboratory.

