4.4. Analysis Visits

Data will be presented and analyzed according to the visit recorded in the database. For other efficacy and safety data that visit are entered, no visit windows will be defined as sites should have case report form (eCRF) instructions and training to ensure reasonable data entry. If a visit happens outside the protocol-defined window (Week X \pm 3 days), one of the following will be occur:

- If it is recorded as Week X visit, no visit re-mapping will be done (except for PRO endpoints and Part B visits) and the recorded visit will be used in all analysis.
- If it is recorded as unscheduled visit, it will be treated as unscheduled visit.

In general, only those assessments which are assigned to an analysis visit will be included in the summary tables and figures and will be presented by visit. Unscheduled visits will not be included in summary tables or figures, with the following exceptions: if the table or figure includes data values for all post-baseline assessments (worst/best/maximum/minimum post-baseline assessments), or for tables which report the values during a period of time, unscheduled visits will be included. All unscheduled visits will be included in the listings.

When reporting results or events that are reported on an ongoing basis, such as cumulative prednisone dose or flare at Week X: All results/events will be taken into account that occur inclusively between the day after the Week X-1 visit and the day of the Week X visit. The actual day of the Week X visit will always be taken into account as the day of visit X, even if the actual visit occurred outside of planned visit window.

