9.2. Clinical Laboratory Evaluations

Clinical laboratory safety test (hematology, serum chemistry, fasting lipids and other tests) will be collected as specified in [Appendix 13.1](#) and will be analyzed by a central laboratory.

All summaries will be based on the standard international units.

Laboratory data will be listed and abnormal values will be flagged in the data listings. A listing of laboratory data outside of normal ranges will be presented by actual treatment group. A listing of laboratory test reference ranges will also be provided. Test reference ranges used will be the references range provided with the lab results.

Summary tables presenting observed values and changes from Baseline will be presented for clinical laboratory tests with numeric values by actual treatment group for subjects in the Safety set, separately for each laboratory category.

The assessment of laboratory toxicities will examine all Common Terminology Criteria for Adverse Events (CTCAE V4.03) gradable laboratory tests. The National Cancer Institute Common Terminology Criteria for Adverse Events (NCICTCAE) will be used to grade laboratory gradable abnormalities. Maximum CTCAE post-Baseline grade will be summarized over time for each CTCAE gradable laboratory parameter. Summary of CTCAE grade shifts from Baseline will also be produced over Time and for the worst post-baseline value. CTCAE grades will be displayed in laboratory listings.

Abnormal (i.e. outside of laboratory test reference ranges) chemistry and hematology values will be summarized by actual treatment. Shift from baseline tables of normal ranges by actual treatment will also be provided for the chemistry and hematology parameters, over time and for the worst-post baseline value.

A summary table for abnormal laboratory tests Alanine Aminotransferase (ALT), Aspartate aminotransferase (AST), Absolute Neutrophil Counts and Platelet Counts will be generated over time and the following abnormal categories will be used:

Table 6 Abnormal Categories for AST, ALT, Neutrophils and Platelet Counts

Test Name	Categories		
AST	≥3 x ULN	≥5 x ULN	
ALT	≥3 x ULN	≥5 x ULN	≥8 x ULN
Neutrophils	<0.5 x 10 ⁹ /L	0.5 to ≤1.0 x 10 ⁹ /L	>1.0 x 10 ⁹ /L
Platelet Counts	<50 x 10 ⁹ /L	50 to ≤ 100 x 10 ⁹ /L	>100 x 10 ⁹ /L

ULN: upper limit of normal

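### SAP Table 6 can miss ALT/AST, neutrophil and platelet threshold values: it takes the last value per scheduled visit, leaves out unscheduled results, and has no worst-post-baseline row

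*SAP*

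**What the plan says.** - **SAP Section 4** sets one rule for repeated measurements in summaries over time: "In case of multiple assessments for a scheduled visit, the last non missing assessment for this visit will be used". It states no exception for safety data. On listings it adds: "Any repeat or additional assessments performed will be included in the individual subject data listings".
- **SAP Section 4.4** says: "Unscheduled visits will not be included in summary tables or figures, with the following exceptions". The exceptions are tables of extremes ("worst/best/maximum/minimum post-baseline assessments") and tables that report values during a period of time. A visit is not re-mapped: "If it is recorded as unscheduled visit, it will be treated as unscheduled visit".
- **SAP Section 9.2** plans a summary of abnormal ALT, AST, "Absolute Neutrophil Counts and Platelet Counts will be generated over time and the following abnormal categories will be used". These are the Table 6 categories: neutrophils <0.5, 0.5 to ≤1.0 and >1.0 × 10⁹/L; platelets <50, 50 to ≤100 and >100 × 10⁹/L; and multiples of the upper limit of normal for AST and ALT, starting at 3. The same section gives the CTCAE-grade shifts and the normal-range shifts both a by-time and a worst-post-baseline version. It gives Table 6 only the by-time version.
- **Protocol Section 7.5.6, Table 7** attaches an action to these thresholds. For platelets it reads: "Interrupt study drug administration, repeat platelet count test as soon as possible". Parallel wording covers neutrophils and ALT/AST, and retests go to the central laboratory.
- **SAP Section 11** repeats the Part A safety summaries for Part B.

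**The concern.** Taking the last value is harmless when repeats are unrelated to the result. Here they are not: the protocol asks for the repeat because the first value crossed a threshold. The later value is then the one more likely to have recovered, and it is the one the table keeps.

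Cytopenia is a named sirukumab risk in protocol Section 4.6.1, which mentions severe thrombocytopenia with bleeding. After termination the SAP restricts efficacy to summary statistics, so the safety tables carry much of the report. At stake is the by-arm count of subjects who reached the laboratory values at which the protocol interrupts or stops study drug. As the plan is worded, that count can depend on how a site labels a retest.

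**Working it through.** No figure in the plan needs reproducing. The check applies the stated rules to one subject.

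**Inputs**
- Within a scheduled visit, use the last non-missing value (SAP Section 4).
- Unscheduled results are left out of by-visit tables and included in worst-value tables (SAP Section 4.4).
- Neutrophil categories come from SAP Table 6, in × 10⁹/L.
- Assumed values: a trigger of 0.8, with a retest of 1.3 (recovered) or 0.4 (worse).

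**Rules as formulas**
- Table 6 category = category of the last value filed under Week 8.
- Worst-post-baseline category = category of the minimum of all values, including unscheduled ones.

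| Case | Filed under Week 8 | Filed as unscheduled | Table 6 | Worst value | Threshold hit missed in Table 6? |
|---|---|---|---|---|---|
| a | 0.8, then 1.3 | none | last = 1.3: >1.0 | min = 0.8: 0.5 to ≤1.0 | Yes, by the last-value rule |
| b | 0.8 | 1.3 | last = 0.8: 0.5 to ≤1.0 | min = 0.8: 0.5 to ≤1.0 | No |
| c | 1.3 | 0.8 | last = 1.3: >1.0 | min = 0.8: 0.5 to ≤1.0 | Yes, by the unscheduled-visit rule |
| d | 0.8, then 0.4 | none | last = 0.4: <0.5 | min = 0.4: <0.5 | No |

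Cases a and c are the two routes to a miss. In Part A, haematology is scheduled every 4 weeks after Week 4, so the next scheduled sample need not recapture a short-lived fall.

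**Size**
- Share of hits missed in Table 6 = share in case a + share in case c. The documents give neither, so the range is 0 to 100%.
- Share missed in the worst-post-baseline tables = 0% in every case.

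**Do the other outputs supply the missing count?**
- *Worst-post-baseline shifts (SAP Section 9.2)* keep the trigger value, but report CTCAE grade or normal-range status. A normal-range shift cannot separate platelets just below normal from platelets ≤100. CTCAE cut-points are not reproduced in the documents, so their match to the action thresholds cannot be checked here.
- *Maximum-ALT plots (SAP Section 9.2) and the liver-event and hepatobiliary summaries (SAP Section 9.6.1)* cover the liver only.
- *Cytopenia events of special interest (SAP Section 9.1.8)* rest on adjudicated adverse events. Under protocol Appendix 4, an abnormal laboratory result counts as an adverse event when the investigator judges it clinically significant. That is not a threshold count.
- *Listings* keep every result but give no rate by arm.

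**The case against.** The strongest reply is that the loss is conditional and local. Nothing in the documents says that retests are filed under the visit that triggered them. A separate later draw recorded as unscheduled is at least as plausible, and it leaves the scheduled trigger in place (case b). Cytopenias are also reported at subject level as events of special interest, with seriousness, severity, outcome and action taken, exposure-adjusted rates and relative risks. Adverse events leading to interruption or discontinuation of the injection are tabulated. Table 6 is one descriptive table in a terminated study; no hypothesis, alpha or efficacy result depends on it.

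Most of this stands and limits the point. It also disposes of two inferences that a reader might draw. One is that either way of filing a retest lowers the count. Cases b and d show otherwise: an unscheduled retest leaves the scheduled trigger counted as a hit, and a worse retest at the same visit is counted in the more severe category. The other is that a confirmed neutrophil count below 0.5 would drop out. Confirmation under protocol Table 7 presupposes a first value already below 0.5, and if that value is the scheduled one it stays in the <0.5 row when the repeat is filed as unscheduled.

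The reply does not supply the missing neutrophil and platelet count. The sponsor might say that Table 6 falls under the exception for tables reporting values during a period of time. The SAP does not say so, and that reading would still leave the last-value rule in force within a scheduled visit.

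**Conclusion.** The point holds for Table 6 alone. As written, a threshold value can be missed there when a recovered retest is filed under the same scheduled visit, or when the hit is found only at an unscheduled draw. How often is unknown: 0 to 100% of hits. The gap matters most for neutrophils and platelets, because the liver criteria have their own subject-level summaries.

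A reader might infer that laboratory safety hits are undercounted across the report. The documents do not support that, because the worst-post-baseline shifts, maximum-ALT plots, liver summaries, special-interest event tables and listings keep the value or the event.

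The conclusion assumes that Table 6 is a by-visit summary, as its wording indicates, and that no retest-filing convention outside these documents overrides the SAP. It carries over to Part B because the Part A safety summaries are repeated there.

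**What to change.** In SAP Section 9.2, state that Table 6 uses the worst value at each visit instead of the last. Add one row per parameter: any time post-baseline (worst value, including unscheduled visits and retests). Apply both changes to Part A and Part B. The same edit could say which visit a retest belongs to, and whether the maximum CTCAE grade summarised over time is the maximum within a visit.

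The cost is one SAP sentence and one row per parameter, with no new data. Reported abnormality counts may be slightly higher.
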